6.3.3 Payment

PPI Payment will follow the NIHR INVOLVE recommended rates. CYP and parents/carers will be paid for their involvement in the focus groups, at a rate of £25 per hour of activity. Professional CAMHS stakeholders will not be offered payment, unless agreed otherwise. We will be asking professional stakeholders to join focus groups during the working day for which they are paid, and therefore we will not be paying them for their time. We have included 'unless agreed otherwise' to allow for a discussion for any individuals who may have to take time out of work to participate, as then we will pay them for their involvement.

7 ETHICAL AND REGULATORY CONSIDERATIONS

The project will require NHS Ethics and HRA approvals, and UREC approval for WP1. As a project team, we have extensive experience completing ethical applications. All our previous NHS Ethics and HRA applications have received approval. We shall address a number of ethical issues throughout the study, including: informed consent, data confidentiality, safety, burden, distress and risk.

7.1 Assessment and management of risk

7.1.1 Consent and Safeguarding

We have extensive experience of obtaining informed consent from participants in digital health research. We shall follow standard ethical procedures for gaining informed consent from participants in research studies. An information sheet and consent form approved by the ethical committee describing the study will be provided to all potential participants.

Consent will be confirmed at the beginning of the focus groups, roundtables, workshops and semi-structured interviews, and participants will be reminded that they can leave the discussion at any time, without giving an explanation. The consultations will be facilitated by at least 2 researchers who will aim to ensure that a friendly and positive environment is created.

Participants may be asked about their experiences with the CAMHS referral system, either as professionals, referrers, parents/carers or CYP themselves.

We do not envisage that the consultations will be distressing for professional participants. For parents/carers or CYP who have had difficult experiences with the referral process, discussing their experiences may be distressing. For this reason, we have developed a distress protocol which the research team will follow if people are affected by the topics within the focus groups and want to seek help. Participants will also have the option to leave to join a breakout room with one researcher if needed. We do not expect there to be significant safety, burden or distress and risk issues to address, therefore research activities are unlikely to cover topics which result in distress. Our digital tool is a supportive referral tool to enable appropriate CAMHS referrals to be made. The tool will contain links to local sources of mental health support, and will clarify that it is not to be used for crisis support. It will contain links to emergency support lines and advise users in distress to contact the relevant support services (GP, A&E, 111).

We do anticipate some CYP and their parents might want to discuss their problems and get advice. We have included in our Information sheet that we are not asking anyone to share details of their own mental health, but based on this feedback, we have made this clearer and included that we will not be offering advice or guidance on the referral process or about people's mental health issues. We will also make sure to include this statement at the beginning of all stakeholder consultations, to remind participants that we are not asking them to share their mental health problems.

7.1.2 Data security, protection and confidentiality

Data security, data protection and confidentiality are particularly relevant to the development and implementation of our CAMHS referral digital tools. The following issues will be addressed:

- Information and research governance and data protection/GDPR compliance will be overseen by the University of Manchester Information Governance team, supplemented by specialist health informatics data security and confidentiality guidance from the Centre for Health Informatics, University of Manchester.
- A data management plan, following University of Manchester policy, will be developed by the project team, and reviewed and updated throughout the lifetime of the project.
- Data access will be strictly controlled and only available to authorised users.
- Data sharing agreements will be established between organisations and sites as required. This will be overseen by the Sponsor (GMMH) and also supported by the University of Manchester Information Governance and Contracts team.
- Embedding the CAMHS referral tools within CAMH sites will be through close collaboration with the IM&T teams at the 5-8 Trusts. All appropriate NHS Information Governance data security standards will be complied with.

- The importance of respecting each other will be discussed with all participants at the start of stakeholder consultations, it will be made clear that they should not talk about what other people have said outside of the discussion. Participants will not be asked to share specific personally identifiable information during the consultations, but they may spontaneously share information.
- The semi-structured interviews will be recorded and transcribed. During transcription, all identifiable information will be removed, and the recording deleted permanently afterwards.
- Focus groups, workshops and roundtables will not be recorded, and members of the research team will take notes during these consultations.

7.1.3 Safety, Burden, Distress and Risks

We do not expect there to be significant safety, burden or distress and risk issues to address: our digital tool is a supportive referral tool to enable appropriate CAMHS referrals to be made. As we have done in other studies, we have developed a distress protocol which the research team will follow if people are affected by the topics within the focus groups and want to seek help. It will contain links to emergency support lines and advise users in distress to contact the relevant support services (GP, A&E, 111).

7.2 Research Ethics Committee (REC) and other Regulatory review & reports

Before the start of the study, a favourable opinion will be sought from a REC on the study protocol, informed consent forms and other relevant documents e.g. advertisements. The Chief Investigator will produce progress reports as required and the Principal Investigator will notify the REC of the end of the study. If the study is ended prematurely, the Principal Investigator will notify the REC, including the reasons for the premature termination. All correspondence with the REC will be retained.

Within one year after the end of the study, the Principal Investigator will submit a final report with the results, including any publications/abstracts, to the REC.

7.2.1 Amendments

For substantial amendments to the REC application or the supporting documents, the research team shall submit a valid notice of amendment to the REC for consideration. The REC will provide a response regarding the amendment within 35 days of receipt of the notice. It is the responsibility of the Sponsor to decide whether an amendment is substantial or non-substantial for the purposes of submission to the REC.

Substantial amendments that require review by the Sponsor will not be implemented until the Sponsor returns an approved amendment form which will then be submitted via IRAS. Any substantial change to an approved project should be submitted for approval as a project amendment. This will be done by the Project Manager via the IRAS system and will be reviewed by the PI. Guidance for how to submit an amendment can be found on the IRAS website under the heading of [Amendment guidance - all review bodies](#). Any substantial amendments will be communicated to the relevant stakeholders at project meetings or via email.

A log of all amendments will be tracked in the protocol to identify the most recent protocol version.

7.3 Peer review

The study underwent independent peer review by research experts in the area by the National Institute for Health Research prior to the Principal Investigator receiving funding for this project.

7.4 Patient and Public Involvement

We will hold bimonthly 1-hour meetings with our Young Persons Advisory Group (YPAG, n=6-10) and quarterly meetings with our Parents/Carers and Professionals Advisory Group (PPAG; n=6-10). We will establish mechanisms for incorporating feedback from these groups into our work, ensuring young people and their parents/carers/families influence decision making.

All potential Young Person's advisory group members will be provided with an Information Sheet and Consent Form via email. The Information Sheet will detail the nature and objectives of the study and will be developed in accordance with NHS guidance. Members will be given sufficient time to understand the information they are given and to weigh up the information in order to make an informed decision. They will be given the opportunity to ask any questions about the research if they want to. The Consent form will be collected prior to them joining the advisory group via email or post. Participation is voluntary and members will be informed that they have the right to withdraw at any time without giving a reason.

PPAG members will not need to complete a consent form.

YPAG and PPAG members will be paid £25 for their attendance at each advisory group meeting (a maximum of 10), both based on the NIHR INVOLVE's guidance.

We will work with our YPAG and PPAG to develop the topic guide for the stakeholder focus groups. We will feed back the discussions of the advisory groups for consideration at the focus groups in an iterative manner to allow the topic content to evolve. Process/pathway mapping outcomes and data analysis will be discussed at the YPAG/PPAG meetings. This will a) ensure the advisory groups are informed about emerging findings b) identify any gaps/problems in the data and analysis c) ensure the direction of the research remains aligned with their priorities. Our PPI groups and activities will be fully supported throughout the project.

7.5 Protocol compliance

Accidental protocol deviations can happen at any time. They must be adequately documented on the relevant forms and reported to the Principal Investigator and Sponsor immediately.

Deviations from the protocol which are found to frequently recur are not acceptable, will require immediate action and could potentially be classified as a serious breach.

7.6 Regulatory Review & Compliance

Before any site can enrol patients into the study, the Principal Investigator or designee will ensure that appropriate approvals from participating organisations are in place. Specific arrangements on how to gain approval from participating organisations are in place and comply with the relevant guidance. Different arrangements for NHS and non NHS sites are described as relevant.

For any amendment to the study, the Principal Investigator or designee, in agreement with the sponsor will submit information to the appropriate body in order for them to issue approval for the amendment. The Principal Investigator will work with sites (R&D departments at NHS sites as well as the study delivery team) so they can put the necessary arrangements in place to implement the amendment to confirm their support for the study as amended.

7.7 Indemnity

This study is sponsored by Greater Manchester Mental Health NHS Foundation Trust and standard GMMH insurance and indemnity will apply.

7.8 Access to the final study dataset

The co-PIs, the Project Manager, the project researchers, the statistician, and the qualitative analyst will have access to the final study dataset. Other members of the research team will be allowed access if a formal request describing their plans is approved by the steering group.

8 DISSEMINATION POLICY

8.1 Dissemination policy

The datasets arising from the study will be protected by know-how, copyright and database rights (which are automatic rights and do not need to be registered). The copyright for the foreground IP will be held by GMMH.

The draft final report will be due to the NIHR two weeks after the end of the contract. The NIHR will contact the team at least three months before this time with more specific advice. Further guidance on writing the draft final report can be found on the Information for Authors webpage. This guidance is regularly updated and will change during the lifespan of the project. We must make sure to use the most up to date guidance when drafting the report.

8.2 Outputs

Key indicators of success will be defined by the following criteria:

- Digital referral platform successfully tested across minimum 5 CAMHS.
- Stakeholders successfully recruited to roundtable events and prioritisation of features consultation.
- CAMHS referral technical standards defined.
- Co-design of digital tool completed with outputs produced and published.
- Quantitative referral data collected and analysed from CAMHS sites. A reduction in the proportion of unsuccessful referrals is achieved when made through the ENCAMS platform compared to the usual referral processes.
- Following AMUsEd framework, engagement and usage metrics with the digital platform demonstrate that the platform is usable and acceptable to referrers.
- Qualitative intervention data successfully collected and analysed. Qualitative interviews demonstrate usability and acceptability of the platform to referrers and key stakeholders, including GPs, school staff, health and educational professionals and CYP and families/carers themselves. Qualitative interviews demonstrate a preference for the platform by referrers and key stakeholders, including GPs, school staff, health and educational professionals and CYP and families/carers themselves.
- Evaluation successfully completed.
- Sustainability plan developed that secures future plan for the CAMHS digital tool supported for use within the NHS.

Specific outputs for WP1

- Report detailing the changing CAMHS landscape (from roundtables) and how the digital tool aligns with newly configured CAMH services.
- Clear set of priorities and requirements for the revised CAMHS referral process, ranked by Must Have, Should Have, Could Have and Won't Have (MoSCoW) to enable the technical build in Work Package 2.
- A set of technical referral standards for the digital tool for development in WP2.

Finally, we aim to produce 4 peer-reviewed academic publications during the project.

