EN-CAMHS 1 stakeholders recommended we implement a digital solution to address the current problems of poor communication, missing information, poor data quality and lack of guidance for families about what to expect of the referral journey. The design and development of the digital tool will specifically address the accessibility needs of referrers. We intend to explore issues of digital accessibility in the consultations (WP1) and in the co-design workshops with participants. We shall also consider the three key elements of digital exclusion: lack of digital access; lack of digital skills; lack of confidence to use digital. We will explore these challenges in the co-design workshops, with stakeholders in consultation and with our advisory groups. The digital tool will supplement rather than supplant traditional modes of referral; traditional (e.g. paper based) modes of referral will remain. However, we anticipate that our digital tool will enable more people to make more successful referrals than before.

We shall also **generate new knowledge** about the patterns of referrals into CAMHS, by automating data collection through the digital tools and thereby enabling services and NHS England to understand referral and treatment data in greater detail than ever before. We see **enormous potential** in this project and its learnings/outputs for cross-pollination to **other services experiencing similar problems**.

1. Referrals overwhelming CAMHS

- We **cannot** increase CAMHS staff levels or change what it can provide.
- We **can** make the referral process work better and with greater satisfaction for referrers and for those being referred.
- We **can** increase confidence in CAMHS alternatives and increase follow-through into CAMHS alternatives.
- We **can** help CAMHS prioritise the needs of those it is designed to help.

2. Quality of referrals is poor

- We **can** provide clear, accessible guidelines to make appropriate referrals.
- We **can** validate input on the referral form and ensure all required information is completed pre-submission.
- We **can** raise awareness about what a good referral is.
- We **can** educate people about common referral mistakes.

3. Poor experience of referral

- We **can** explain the referral process clearly.
- We **can** outline key steps in the referral journey and inform people about the expected waiting times for the local CAMHS triage process.

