3 RESEARCH QUESTION/AIM(S)

Our overarching aim is to improve the CAMHS referral process for CYP, their families and carers, as well as for health, education and CAMHS professionals so that CYP receive the help they need as quickly as possible.

Research questions:

1. Using the findings from EN-CAMHS 1 and stakeholder consultation, can we develop a set of national standards for digital CAMHS referral processes?
2. Can we translate the prioritised features from EN-CAMHS 1 of a digitally-led, intelligent CAMHS referral process into a usable, acceptable and widely accessible platform that is nationally standardised, locally adaptable and sustainable?
3. Can we address concerns about digital exclusion and other identified health inequalities through the newly developed CAMHS referral mechanisms?
4. How do referrers, including GPs, school staff and children/young people/families perceive the usability and acceptability of the digital tool?
5. How do referrers use and engage with the tool?
6. How do rates of successful referrals with the tool compare to traditional modes of referral?

There are no primary nor secondary outcome measures for this study as this is a feasibility study to evaluate usage and acceptability of the co-created tool using data collected from referrers. These data will be a combination of quantitative data on usage and engagement and qualitative data from semi-structured interviews with 25 referrers.

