- Discovery [38]: The discovery phase will draw heavily on the findings of ENCAMS 1 and of Work Package 1 of this project. We shall translate these findings into outputs that can be disseminated widely including User Personas (to indicate the profiles of different referrers who will use the system) and User Journey Maps (to show how people will interact with the system at each stage of the process).
- Alpha [39]: Our senior designer will produce prototypes and wireframes to demonstrate the flow of the digital tool in this phase for feedback and review by workshop participants.
- Beta [40]: During this phase, we shall ask at least 5 healthy volunteers to try out the newly-developed tool to ensure it has no critical or major defects and is ready for use in the evaluation in WP3.
- Live [41]: The live version of the platform will be demonstrated in a co-design workshop available for participants to try and provide feedback.

A priority for the digital tool is to be inclusive and accessible to all. We will work collaboratively with our stakeholder groups during the co-design phase to ensure we maximise the accessibility of the tool. From EN-CAMHS 1 we already know that supporting access to translated materials is an important requirement. We aim to go well above and beyond the WCAG 2.2 standards [31] to ensure that the tool we develop has as wide a reach as possible. We shall also beta-test the accessibility with a Digital Accessibility Working Group.

Work Package 3 (WP3): (KMA, PW, VB, LAC, PB, RE, PB) Months 12-24 - Evaluation of Implementation

We aim to:

- Evaluate implementation of the new digitally-enhanced referral process with 60 key referrers.
- Explore the potential, enablers and barriers of embedding a new CAMHS referral mechanism via semi-structured qualitative interviews with 25 referrers.
- Develop a blueprint and toolkit for CAMHS to implement the referral tool.
- Understand if and how the tool enhances the CAMHS referral process.

A mixed-methods, non-randomised evaluation of implementation with 60 CAMHS referrers across 5-8 CAMHS. CAMHS sites and referrers will be chosen to reflect the diversity of the current CAMHS landscape. 9 CAMHS sites have indicated their support for working with us on the evaluation. We shall evaluate usage and acceptability data collected from referrers which combine quantitative data on engagement and usage with qualitative data from semi-structured interviews with 25 referrers.

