We shall use the NASSS-CAT toolkit [32] to guide the implementation and evaluation of the digital tool across CAMHS sites. This entails running a NASSS-CAT workshop with key stakeholders from each CAMHS service in order to introduce and complete the assessment as well as create a risk management and mitigation plan. The workshop will identify gaps in information that will need to be identified and incorporated. Once this is done, the risk plan will be regularly reviewed throughout the implementation process. Insights from this will be turned into an implementation toolkit that sets out a standardised evidence-based approach along with common risks and how they can be managed or mitigated. We shall also use the NASSS-CAT implementation toolkit to explore the potential, enablers and barriers of embedding a new CAMHS referral mechanism across different types of referrers and across CAMHS with various configurations. The NASSS-CAT toolkit will be used to guide implementation discussions with key stakeholders. Specifically, we will use the NASSS framework to address key considerations for the implementation digital transformation covering the key NASSS areas: the illness/condition in question; the technology; the value proposition; the intended adopters; the organisation; external context for innovation. The questions from the NASSS-CAT toolkit on these areas will be tailored for the EN-CAMHS project and used to structure the topic guides for interviewers with referrers.

We shall collect referral data from each referrer and from the CAMHS site referred into. We shall collect number of referrals made via the digital tools and numbers made by traditional referral mechanisms. We shall collect usage and engagement data with the tool, including numbers of referrals completed to an endpoint (either referral sent to CAMHS or to alternative help). We shall collect data on accepted/rejected referrals made by participant referrers to CAMHS using a) the tool and b) traditional modes of referral. Co-design workshops with each CAMHS provider will help us understand which data can be captured, and how each provider records the data.

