6.3 Recruitment

6.3.1 Sample identification

In WP1, we shall hold a combination of stakeholder specific and mixed stakeholder groups. Attendees can choose which type of group they feel most comfortable attending. Across the 6 focus groups we aim to recruit 60 participants representing a diversity of referrer type (CYP, GP, health, social care, educational professional, CAMHS workers, families), and also designed to incorporate the diversity within each referrer type found in EN-CAMHS 1. Identification and recruitment of stakeholders will be extensively supported by our partner MQ.

In WP3, we shall recruit referrers from across the study CAMHS sites. Senior stakeholder collaborators will be consulted to ensure the project achieves the most appropriate mix of CAMHS providers to optimise widespread applicability of the new tool. We shall work with 60 referrers to test the new referral process. We shall specifically aim to ensure appropriate diversity to test if the translated and culturally-sensitive materials we develop are fit for purpose.

We have not used power calculations for detecting effect sizes in this evaluation, as hypothesis testing is not the aim. Our aims are to 1) recruit participants to test different user experiences (opportunities and challenges) that arise as a result of using tool and; 2) to capture a diversity of: referrer types (GPs, school staff, social care professionals, parents/carers); within-referrer characteristics (age, gender, ethnicity, dis/ability); CAMHS provider (CAMHS configuration; rural/urban). Our purposive sampling approach will be targeted at maximising the diversity of referrers and CAMHS sites and supporting accessibility testing of the tool. Our sampling strategy will be informed by our diversity data from EN-CAMHS 1 and by the stakeholders consultations in WP1.

Identification and recruitment of CAMHS professional stakeholders will be supported by our extensive network of CAMHS collaborators. Recruitment of key referrers is supported by our school and primary care collaborators, as well as links to key referrers provided by our CAMHS sites. We will not directly target individuals, just share adverts about the study around collaborating organisations and networks.

Recruitment of CYP and their families will be supported by our CAMHS networks, adverts on social media and websites, and our third sector collaborators (MQ, Calm Connections, Anna Freud Centre).

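### Section 8.2 counts an achieved reduction in unsuccessful referrals as a criterion of success, in a non-randomised feasibility study with no power calculation that cannot support that verdict

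*Protocol*

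**What the plan says.** Section 8.2 of the protocol introduces a list of nine bullets with "Key indicators of success will be defined by the following criteria". The bullet on quantitative referral data asks first that the data be collected and analysed, then adds: "A reduction in the proportion of unsuccessful referrals is achieved when made through the ENCAMS platform compared to the usual referral processes".

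Other sections describe a study of a different kind:

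- Section 3: "There are no primary nor secondary outcome measures for this study as this is a feasibility study to evaluate usage and acceptability".
- Section 4.1, Work Package 3: "A mixed-methods, non-randomised evaluation of implementation with 60 CAMHS referrers across 5-8 CAMHS".
- Section 6.3.1: "We have not used power calculations for detecting effect sizes in this evaluation, as hypothesis testing is not the aim".
- Section 2: "The digital tool will supplement rather than supplant traditional modes of referral".
- Section 4.1 again: "We shall collect data on accepted/rejected referrals made by participant referrers to CAMHS using a) the tool and b) traditional modes of referral".

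Research question 6 is neutral about direction: "How do rates of successful referrals with the tool compare to traditional modes of referral". Section 4.2 likewise plans only to set one rate against the other. Section 3.2 names a greater proportion of successful referrals among effects the team hopes for. Only Section 8.2 makes a favourable direction part of the definition of success.

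**The concern.** The criterion is a comparative result that must come out in the tool's favour. The design gives it no support, for two reasons.

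- **Chance.** The number of referrals was not chosen to give any precision, and the criterion names neither a size nor an uncertainty.
- **Selection.** Both routes stay open, and nothing says which child's referral goes by which route. If simpler or better-documented cases tend to go through the tool, its percentage of unsuccessful referrals will be lower even if the tool does nothing.

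Followed as written, the study could report as a success that the platform reduced unsuccessful referrals when the difference is chance or case mix. It could equally count itself unsuccessful on this point when the tool does help. The indicator is not a stop/go rule and affects no participant's care. What is at stake is what the study may conclude, in a project that intends to inform national policy and roll-out.

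**Working it through.** The protocol states no power, significance level, effect size or referral count, so there is no figure of its own to reproduce. The calculation below shows how the criterion would behave.

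**Inputs**

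- 60 referrers (Section 4.1 and Section 6.2.1).
- Background unsuccessful rate just under one in four (Section 1). I used 25%, with 10% and 40% as a range.
- Assumed: 1, 2 or 5 referrals per referrer per route, which gives n = 60, 120 or 300 per route. Referrals are independent unless stated.
- Assumed for illustration: a 5-point difference, 20% with the tool against 25% by traditional routes.

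**Reading 1: any observed reduction counts.** With X_tool and X_trad independent binomial counts, P(success) = Σₓ P(X_trad = x) · P(X_tool ≤ x − 1).

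| True unsuccessful rate, tool v traditional | n = 60 | n = 120 | n = 300 |
|---|---|---|---|
| 10% v 10% | 43.9% | 45.7% | 47.3% |
| 25% v 25% | 45.8% | 47.0% | 48.1% |
| 40% v 40% | 46.3% | 47.4% | 48.3% |
| 20% v 25% | 70.8% | 80.3% | 92.2% |

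In the first three rows the tool has no effect, yet it passes nearly half the time. If the 5 points in the last row come from selection alone, that tool also has no effect, and more data make the false success more likely.

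**Reading 2: the 95% confidence interval must lie wholly below zero.** Success requires p̂_tool − p̂_trad + 1.96·√{[p̂_tool(1 − p̂_tool) + p̂_trad(1 − p̂_trad)]/n} < 0, summed over the exact joint distribution.

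| True unsuccessful rate, tool v traditional | n = 60 | n = 120 | n = 300 |
|---|---|---|---|
| 10% v 10% | 3.0% | 2.7% | 2.5% |
| 25% v 25% | 2.7% | 2.6% | 2.5% |
| 40% v 40% | 2.6% | 2.8% | 2.5% |
| 20% v 25% | 10.0% | 15.5% | 31.3% |

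The last row has two interpretations. If the 5 points are selection, it is the chance of a false success. If they are a real effect, the criterion misses it 90.0%, 84.5% or 68.7% of the time (100% minus the row).

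**Precision.** The half-width of the 95% interval at 25% on both routes is 1.96·√(2 × 0.25 × 0.75 / n):

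- n = 60: 1.96·√0.00625 = 15.5 points
- n = 120: 1.96·√0.003125 = 11.0 points
- n = 300: 1.96·√0.00125 = 6.9 points

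Repeated referrals by one referrer can move this either way. The within-referrer correlation ρ is assumed to be 0.05 to 0.125.

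- All 60 referrers use both routes equally: multiply by √(1 − ρ). Half-widths become 14.5-15.1, 10.2-10.7 and 6.5-6.8 points.
- 30 referrers use only one route and 30 only the other, with 2k referrals each (k = 1, 2, 5): multiply by √(1 + (2k − 1)ρ). Half-widths become 15.9-16.4, 11.7-12.8 and 8.3-10.1 points.

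Under every one of these assumptions the half-width exceeds 5 points.

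**The case against.** The strongest reply is that this is half of one bullet in an outputs list within the dissemination section, mostly made up of deliverables. Nothing ties it to a continuation decision, and the sections that govern inference are sound. That bears on how serious the point is. It does not remove the direction, because the list says that success is defined by these items and no other section qualifies it.

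A statistical analysis plan, not shown here, might supply a decision rule. The two readings above are unadjusted, and a within-referrer analysis could remove differences between referrers. True, but it would not handle a referrer's choice of route for each child, nor would it supply planned precision.

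The sizes rest on assumptions. Selection could run against the tool: at 30% v 25%, Reading 1 gives 24%, 17% and 8%. The comparator could also be larger if sites contribute all their usual referrals. With an assumed 3,000 comparator referrals, the half-widths fall to 11.1, 7.9 and 5.1 points. Both points stand as limits on the figures. Reverse selection, however, makes the verdict wrong in the other direction, and a larger comparator leaves a no-effect tool passing about half the time under Reading 1.

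Two further remarks are fair. The meaning of unsuccessful is unsettled: Section 4.2 counts a referral to alternative support as successful, while Section 4.1 collects acceptance or rejection by CAMHS. Other bullets in Section 8.2 also presuppose favourable findings. Neither is a reason to keep this criterion.

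**Conclusion.** The concern holds. Section 8.2 fixes a favourable comparative effect as a criterion of success, which contradicts the protocol's own description of the study. The comparison is a proper part of the study, and doing without a power calculation is acceptable in a feasibility study. The fault is the required direction.

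Taken literally, the criterion is close to a coin toss for a tool with no effect, if the routes are comparable and referrals independent. A modest imbalance in case mix turns it into a likely false success or a likely false failure, depending on its direction. Requiring a confidence interval below zero controls chance but not selection, and would usually miss a real 5-point reduction at the numbers assumed. The referral counts, the 5-point difference and the within-referrer correlations are assumptions. The conflict between sections does not depend on them.

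**What to change.** In Section 8.2, keep the requirement that referral data be collected and analysed, and replace the directional sentence with wording such as: *the difference in the proportion of unsuccessful referrals, tool minus traditional, is estimated and reported with a 95% confidence interval that allows for repeated referrals by the same referrer*. Require no direction.

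In Section 4.2, add that the comparison is non-randomised and descriptive and is not by itself evidence that the tool reduces unsuccessful referrals. While editing, make sure that unsuccessful has one meaning in Sections 4.1, 4.2 and 8.2, so that the interval refers to a defined quantity.

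The cost is two sentences plus that definition, and a little analysis work for the interval. Sample, data collection and timetable are unchanged, and research question 6 is still answered. The sponsor gives up a favourable success claim that the design could not support.
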